## 2 STUDY OBJECTIVES

### 2.1 Primary

Assess any ECG changes during standard HyBryte photodynamic therapy.

Assess the systemic blood levels of hypericin during standard HyBryte photodynamic therapy.

### 2.2 Secondary

Assess the safety of HyBryte photodynamic therapy.

## 3 STUDY ENDPOINTS

This is an exploratory study to confirm the low-level systemic exposure to hypericin and the associated potential for any ECG changes. Given the small size of the study and its open label design, no formal efficacy assessments will be performed.

### 3.1 Primary

The primary endpoints for the study are:

Serial assessments of ECG (including QT interval and QT interval corrected for heart rate using both the Bazett's and Fridericia formulas) will be obtained at the same timepoints as serum hypericin samples as follows:

- a. Baseline prior to drug application
- b. Week 4, Session 2 obtained immediately before and 2 hours after the light session
- c. Week 6, Session 2 obtained immediately before the light session
- d. Week 8, Session 2 Light Session visit obtained immediately before and 2 hours after the light session
- e. Week 10 follow-up visit

Serial measurements of serum hypericin levels obtained at:

- f. Baseline prior to drug application
- g. Week 4, Session 2 obtained immediately before and 2 hours after the light session
- h. Week 6, Session 2 obtained immediately before the light session

- i. Week 8, Session 2 Drug Application visit immediately prior to the drug application
- j. Week 8, Session 2 Light Session visit obtained immediately before and 2 hours after the light session
- k. Week 10/End of Study during the follow-up visit

These levels will be correlated with amount of drug applied by the patient estimated by weighing the drug jars at each light session.

### **3.2 Secondary**

Routine safety laboratory investigations and vitals will be obtained at baseline prior to drug application, at Week 8, Session 2 Light Session visit prior to light therapy and 2 weeks after the completion of therapy (Week 10 follow-up visit/End of Study).

## **4 STUDY PLAN**

### **4.1 Study Design**

This study is an observational, Phase 2a trial. Patients will receive treatments twice a week consisting of drug application followed 18-24 hours later with a light session (using Daavlin Series 7 Phototherapy Device with visible light lamps) for 8 weeks (up to 16 total treatments). The light treatment will be performed at least 2 calendar days apart each week. Light treatment is not permitted on consecutive days. Blood samples for evaluation of serum hypericin concentration will be obtained at baseline, Week 4, Week 6, Week 8, and 2 weeks after the last light session (Week 10/End of Study), and ECGs will be obtained at baseline, Week 4, Week 6, Week 8, and the Week 10 follow-up visit. Safety laboratory tests and vital signs will be obtained at baseline, at the end of treatment (Week 8), and at the end of the 2-week follow-up period (Week 10/End of Study).

## 4.2 Schedule of Assessments

Subjects will be screened within 28 days of enrollment. Detailed timing of the assessments is shown in [Table 3](#).

**Table 3: Schedule of Assessments**

Time point	Blood Hypericin Concentration	ECG 	Light Session 	CAILS Evaluations	mSWAT	PGA	VAS itch	Skindex-29 QoL	Safety Assessments 	AE Collection
Screening 										
Baseline 	X 	X 		X 	X 		X 	X 	X 	
Week 1, Session 1			X				X			X
Week 1, Session 2			X				X			X
Week 2, Session 1			X				X			X
Week 2, Session 2			X				X			X
Week 3, Session 1			X				X			X
Week 3, Session 2			X				X			X
Week 4, Session 1			X				X			X
Week 4, Session 2	X  X 	X  X 	X				X			X
Week 5, Session 1			X				X			X
Week 5, Session 2			X				X			X
Week 6, Session 1			X				X			X
Week 6, Session 2	X 	X 	X				X			X
Week 7, Session 1			X				X			X
Week 7, Session 2			X				X			X

Time point	Blood Hypericin Concentration	ECG 	Light Session 	CAILS Evaluations	mSWAT	PGA	VAS itch	Skindex-29 QoL	Safety Assessments 	AE Collection
Week 8, Session 1			X				X			X
Week 8, Session 2 Drug Application	X 									X
Week 8, Session 2 Light Session	X  X 	X  X 	X				X	X	X 	X
Week 10/End of Study	X	X		X	X	X	X		X	X

 ECG will include a standard 12-lead reading with QT interval measurements. Correction for heart rate will be performed electronically using both the Bazett's and Fridericia formulas

 Light Session: Includes application of drug 18-24 hours earlier by the patient and the Erythema Scoring performed 5-10 minutes before and after light therapy

 Safety Assessments: consists of vital signs, and hematology and clinical chemistry blood tests

 The following assessments will be performed at the Screening visit: Obtain Informed Consent Form (ICF) signature, Assessment of entry criteria, Complete Medical History, Vital Signs, Serum HCG pregnancy test (women of childbearing age only)

 Baseline: Includes interval medical history from screening, Complete Physical Examination, review of the results of the serum pregnancy test for eligible female subjects, and charting of index lesions onto the Body Lesion Diagram.

 Obtained prior to drug application

 Prior to light session

 2 hours after completion of the light session

## 5 POPULATION

### 5.1 Number of Subjects

Approximately 6 subjects will be enrolled.

### 5.2 Selection of Subjects

#### 5.2.1 *Inclusion Criteria*

In order to be enrolled into the trial, subjects must meet ***all*** of the criteria below:

1.  $\geq 18$  years of age
2. Active treatment-accessible CTCL lesions covering  $\geq 10\%$  of their body surface area
3. Subjects must have a clinical diagnosis of cutaneous T-cell lymphoma (CTCL, mycosis fungoides), Stage IB or Stage IIA
4. Subjects willing to follow the clinical protocol and voluntarily give their written informed consent
5. Female subjects not pregnant nor nursing and willing to undergo a pregnancy test within 30 days prior to treatment initiation

#### 5.2.2 *Exclusion Criteria*

In order to be enrolled into the trial, subjects ***cannot*** have any of the following criteria:

1. History of allergy or hypersensitivity to any of the components of HyBryte
2. Pregnancy or mothers who are breast-feeding
3. Males and females not willing to use effective contraception
4. Subjects with history of sun hypersensitivity or photosensitive dermatoses (e.g., porphyria, systemic lupus erythematosus (SLE), Sjogren's syndrome, etc.)
5. Subjects whose condition is spontaneously improving
6. Subjects receiving topical steroids or other topical treatments (e.g., nitrogen mustard) on index lesions for CTCL within 2 weeks of enrollment

7. Subjects receiving systemic steroids, psoralen ultraviolet A (UVA) radiation therapy (PUVA), narrow band ultraviolet B (UVB) light therapy (NB-UVB) or carmustine (BCNU) or other systemic therapies for CTCL within 3 weeks of enrollment
8. Subjects who have received electron beam irradiation within 3 months of enrollment
9. Subjects with a history of significant systemic immunosuppression
10. Subjects taking other investigational drugs or drugs of abuse within 30 days of enrollment
11. Subject has any condition that, in the judgment of the principal investigator (PI), is likely to interfere with participation in the study
12. Subjects receiving drugs known to cause photosensitization within 2 weeks of starting HyBryte therapy unless they have not had evidence of photosensitization after receiving a stable dose of the medication for a minimum of 4 weeks

### **5.3 Study Procedures by Time Point**

#### **5.3.1 Screening Visit**

The screening visit must be done within 28 days prior to the start of the Baseline visit. Prior to starting the study medication, the results of all tests must be reviewed to assure that the patient meets all entry criteria. Procedures to be done at this visit are:

Obtain Informed Consent Form (ICF) signature

Assessment of entry criteria

Complete Medical History

Vital Signs

Serum HCG pregnancy test (women of childbearing age only)

#### **5.3.2 Baseline**

After enrollment but prior to application of HyBryte the following assessments will be performed:

Interval medical history from screening obtained

Complete Physical Examination

Vitals taken (heart rate, respiratory rate, and sitting blood pressure)

Hematology panel drawn

Clinical chemistry panel drawn

Pregnancy test results reviewed

Three lesions that are representative of the patient's disease and are discrete with defined borders, will be chosen as the index lesions, and classified as patch or plaque lesions

Charting of all CTCL lesions on the "Body Lesion Diagram" form ([Appendix II](#)) locating and numbering each of the index lesion

Each of the index lesions will have a CAIIS score assessed and recorded

The mSWAT score will be assessed and recorded

5 mL of blood obtained and processed for serum hypericin levels

12-lead ECG obtained including QT interval measurements

The patient will complete the Skindex-29 ([Appendix III](#)) and VASitch forms and the data transcribed into the eCRF

A jar of ointment will be issued and the weight of the jar prior to dispensation will be recorded

Only after all of the above have been completed, patients will be instructed on proper drug application and demonstrate proficiency in drug application and all accessible lesions will be treated with study drug

The weight of the jar after drug application will be recorded

### **5.3.3     Week 1, Session 1; Week 1, Session 2; Week 2 Session 1; Week 2, Session 2; Week 3, Session 1; Week 3, Session 2; Week 4, Session 1**

18-24 hours after drug application, the patient will return to clinic for their light session using the Daavlin 7 Series Phototherapy Device with visible light lamps. At that visit the following will be performed:

The patient will complete an VASitch form and the data transcribed into the eCRF.

Adequate application of the drug will be verified by a pink staining on visual inspection of lesions.

Each patient will bring in their jar of study drug to the clinic. The jar will be weighed by clinic staff in order to estimate the amount of drug applied.

5-10 minutes **before** the light session, lesions will be graded using the Erythema Grading Score.

During the first session, 5 J/cm^2 of light will be administered. Subsequent light sessions will deliver light doses based on the Erythema Grading Score after the previous light treatment. If the Erythema score was <1, the next light dose should be increased as deemed appropriate by the PI. If the Erythema score is 1, the subsequent dose should be held at the same dose. If the score is >1, the next dose should be lowered.

The patient will undergo the light treatment (may require repositioning to assure that all lesions are being treated).

5-10 minutes **after** completion of the light session, lesions will be graded using the Erythema Grading Score. If the score is <1, the light dose should be increased in the next light session. If the Erythema score is 1, the subsequent dose should be held at the same dose. If the score is >1, the next dose may be lowered by at least 1 J/cm^2.

Patients will be asked about any AEs experienced since the last light session and these will be recorded in the eCRF. Information on all unresolved, previously reported AEs will be obtained.

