## STUDY SYNOPSIS

Name of Sponsor/Company: Soligenix, Inc.	(For National Authority Use only)			
Name of Finished Product HyBryte™				
Name of Active Ingredient Hypericin (0.25% ointment)				
Title of Study: Phase 2a Study of Systemic PK and Serial ECG Determinations Following 8 Weeks of HyBryte Treatment				
Investigators: [name]; potentially one additional TBD Investigator				
Study Centre(s): Rochester Skin Lymphoma Center; 1 other site TBD				
Publication (reference): N/A				
Study Period (years): 0.4 year	Phase of Development: Phase 2a			
Date of First Enrollment: 02 May 2022				
Date of Last Completed: 31 October 2022				
Objectives: The primary objectives of this study are to assess: 
 
• the systemic blood levels of hypericin during 8 weeks of standard HyBryte photodynamic therapy; and
 
• any ECG changes during 8 weeks of standard HyBryte photodynamic therapy.
 
				
Methodology: This will be an open label trial. Subjects with CTCL (stage IB or IIA) with lesions of ≥10% of body surface area will be enrolled and receive topical HyBryte applied to all accessible lesions twice per week followed by visible light treatment 18-24 hours later starting at 5 J/cm  and titrated up at each visit until there is evidence of mild erythema of the treated lesions following the light session (Grade 1 erythema on the Erythema Score). At baseline and at the end of weeks 4, 6, 8, and 10, serum for Hypericin levels will be obtained and 12-lead ECG's will be performed at baseline (prior to drug application), at Week 4, Session 2 (immediately before and 2 hours after completion of the light session), at Week 6, Session 2 (immediately before the light session), Week 8, Session 2 Light Session visit (immediately before and 2 hours after completion of the light session), and Week 10/End of Study visit. Routine safety laboratories (hematology, clinical chemistries) will be analyzed at baseline, at the Week 8 Session 2 Light Session visit, and 2 weeks after completion of therapy (Week 10/End of Study). AE's will be recorded throughout the study.				
Number of patients (planned): Approximately 6 subjects will be recruited				

Name of Sponsor/Company: Soligenix, Inc.		(For National Authority Use only)
Name of Finished Product HyBryte™		
Name of Active Ingredient Hypericin (0.25% ointment)		

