### **5.3.4 Week 4, Session 2**

18-24 hours prior to the scheduled light session, the patient will be instructed to apply study drug to all accessible lesions. At that visit the following will be performed:

The patients will complete an VASitch form and the data transcribed into the eCRF.

**Prior** to the light session, 5 mL of blood obtained and processed for serum hypericin levels.

**Prior** to the light session, a 12-lead ECG obtained including QT interval measurements.

Adequate application of the drug will be verified by a pink staining on visual inspection of lesions.

Each patient will bring in their jar of study drug to the clinic. The jar will be weighed by clinic staff in order to estimate the amount of drug applied.

5-10 minutes **before** the light session, lesions will be graded using the Erythema Grading Score.

The patient will undergo the light treatment (may require repositioning to assure that all lesions are being treated).

5-10 minutes after completion of the light session, lesions will be graded using the Erythema Grading Score. If the score is <1, the next light dose should be increased. If the Erythema score is 1, the subsequent dose should be held at the same dose. If the score is >1, the next dose should be lowered by at least 1 J/cm^2.

2 hours after completion of the light session, 5 mL of blood obtained for serum hypericin levels.

2 hours after completion of the light session, 12-lead ECG obtained including QT interval measurements.

Patients will be asked about any AEs experienced since the last light session and these will be recorded in the eCRF. Information on all unresolved, previously reported AEs will be obtained.

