### **5.3.5 Week 5, Session 1; Week 5, Session 2; Week 6, Session 1**

18-24 hours prior to the scheduled light session, the patient will be instructed to apply study drug to all accessible lesions. At that visit the following will be performed:

The patients will complete an VASitch form and the data transcribed into the eCRF.

Adequate application of the drug will be verified by a pink staining on visual inspection of lesions.

Each patient will bring in their jar of study drug to the clinic. The jar will be weighed by clinic staff in order to estimate the amount of drug applied.

5-10 minutes before the light session, lesions will be graded using the Erythema Grading Score.

The light duration for the session to deliver the target dose of light determined by the Erythema Score of the previous treatment response of light will be calculated.

Patients will undergo the light treatment (may require repositioning to assure that all lesions are being treated).

5-10 minutes after completion of the light session, lesions will be graded using the Erythema Grading Score. If the score is <1, the next light dose should be increased. If the Erythema score is 1, the subsequent dose should be held at the same dose. If the score is >1, the next dose should be lowered by at least 1 J/cm^2.

Patients will be asked about any AEs experienced since the last light session and these will be recorded in the eCRF. Information on all unresolved, previously reported AEs will be obtained.

### 5.3.6 Week 6, Session 2

18-24 hours prior to the scheduled light session, the patient will be instructed to apply study drug to all accessible lesions. At that visit the following will be performed:

The patients will complete an VASitch form and the data transcribed into the eCRF.

Prior to the light session, 5 mL of blood obtained and processed for serum hypericin levels.

Prior to the light session, a 12-lead ECG obtained including QT interval measurements.

Adequate application of the drug will be verified by a pink staining on visual inspection of lesions.

Each patient will bring in their jar of study drug to the clinic. The jar will be weighed by clinic staff in order to estimate the amount of drug applied.

5-10 minutes before the light session, lesions will be graded using the Erythema Grading Score.

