#### **6.1 Light Session**

The amount of visible light to be delivered will start at 5 J/cm^2 and be titrated up until either the patient experiences a mild (Erythema Grade 1) response to the light treatment 5-10 minutes post-treatment or a dose of 25 J/cm^2 is reached, whichever occurs first. The

duration of light treatment is dictated by the light treatment table listed below ([Table 4](#)). Depending on the distribution of the patient's lesions, more than one position for light treatments may be necessary.

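### Protocol 5.3.3 gives two different rules for the next light dose after erythema above Grade 1, and a reduction from the starting dose has no row in Table 4

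*Protocol*

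**What the plan says.** **Response to a score above 1.** Protocol 5.3.3 covers Week 1 Session 1 to Week 4 Session 1. Its paragraph on setting the dose says "If the score is >1, the next dose should be lowered" and ends there, with no step size. Its paragraph on grading after the session says "If the score is >1, the next dose may be lowered by at least 1 J/cm" (J/cm²). From Week 4 Session 2 (5.3.4) through 5.3.7 the wording is "If the score is >1, the next dose should be lowered by at least 1 J/cm" (J/cm²).

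**Starting dose and table.** Section 5.3.3 fixes the start: "During the first session, 5 J/cm" (J/cm²). Section 6.1 says the "duration of light treatment is dictated by the light treatment table listed below", meaning Table 4, which runs from 5 to 25 J/cm².

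**Upper limit.** Section 6.1 ends titration at Grade 1 erythema or when 25 J/cm² "is reached, whichever occurs first". SAP 3 gives the same maximum. The synopsis has the dose "titrated up at each visit until there is evidence of mild erythema of the treated lesions following the light session" and gives no limit; neither does 1.4.1. The visit rules are of the form "If the score is <1, the next light dose should be increased", without reference to 6.1.

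**The concern.** On the grading scale in Table 11, a score above 1 is a moderate or worse reaction, which is where site staff most need a single instruction. In 5.3.3 two staff members could each follow the text and act differently: one lowers the dose, the other treats lowering as optional. If a patient reacts this way at the first session, the instructed reduction leads to a dose for which the prescribed table gives no exposure time. At stake are consistent treatment after a more-than-mild reaction and the meaning of the light-dose descriptions planned in SAP 4.3 and 6.3.

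**Working it through.** **1. Do the two sentences in 5.3.3 concern the same score?** Yes. The dose-setting paragraph bases each dose on the grading made after the preceding light treatment, and the later paragraph acts on the grading made 5 to 10 minutes after the session. These are the same measurement, used for the same decision.

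**2. The rules side by side, for a score above 1**

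| Protocol section | Sessions | Strength | Minimum step |
|---|---|---|---|
| 5.3.3, dose-setting paragraph | 7 | should | none stated |
| 5.3.3, post-session paragraph | same 7 | may | 1 J/cm² |
| 5.3.4 | 1 | should | 1 J/cm² |
| 5.3.5 | 3 | should | 1 J/cm² |
| 5.3.6 | 1 | should | 1 J/cm² |
| 5.3.7 | 3 | should | 1 J/cm² |
| 5.3.9 (final session) | 1 | no later dose | not applicable |

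Count: 5.3.3 covers 3 weeks × 2 sessions + 1 = 7. Total: 7 + 1 + 3 + 1 + 3 + 1 = 16.

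**3. Table 4 reproduced.** The first row is 10:49 = 649 s at 5 J/cm², and the last is 54:07 = 3,247 s at 25 J/cm². Fitting duration = k × dose through the origin to all 21 rows gives k = 129.87 s per J/cm², and every row fits to within 0.5 s. The table is internally consistent.

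**4. Lower end.** The starting dose equals the lowest row. Under the wording with a minimum step, the next dose after a score above 1 at the start is at most 5 − 1 = 4 J/cm². Under the wording without one, it is some value below 5. Neither has a row. This can happen after session 1. A time can be extrapolated (for example 4 × 129.87 = 519.5 s), but that shows only that the arithmetic is possible, not that such a dose is intended.

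**5. Upper end.** The visit rules and 6.1 clash literally only for a patient already at 25 J/cm², with a score below 1 and a session still to come. That requires reaching 25 by session 15, so a mean upward step of at least (25 − 5) / 14 = 1.43 J/cm². The documents leave the step to the investigator. Under assumed constant steps:

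| Assumed step (J/cm²) | Result |
|---|---|
| 1 | 5 + 15 × 1 = 20 at session 16; limit not reached |
| 2 | 25 at session 11 |
| 3 | 25 at session 8 (last step cut at 25) |
| 5 | 25 at session 5 |

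**The case against.** *Should* is not *must*. The protocol uses *must* and *will* for firm requirements and says outright that light on consecutive days is not permitted. Every version of the rule points downward, and the single *may* looks like a drafting slip. This stands to the extent that a reader who infers a conflict between a mandatory and an optional reduction goes too far. What remains is a directive sentence against a permissive one for the same score, and a minimum step that is absent, optional or directive depending on the sentence.

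On the table, the fair reply is that it is linear, that the synopsis meters light by exposure time, and that 5.3.5, 5.3.6 and 5.3.9 speak of calculating the duration. So the missing row does not make an exposure time impossible to find. But 5.3.3, where the gap first arises, has no such wording, no formula is given, and 6.1 makes the table the source.

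A reader might also infer that the documents disagree on whether there is a ceiling. They do not support that. No text denies a limit or names another one, and 6.1, SAP 3 and the top row of Table 4 agree on 25 J/cm². The shorter statements omit it and can be read together with 6.1.

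Nor do the documents show that most titration falls in the sessions under 5.3.3. At a constant 1 J/cm² per session, a patient would still be rising at session 16. Seven is the number of sessions the section covers, not an expected number of affected decisions; the documents give no frequency for scores above 1.

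**Conclusion.** The contradiction in 5.3.3 holds on the text alone. For 7 of 16 sessions, the protocol both directs and merely permits a reduction after a score above 1, and it differs from 5.3.4 to 5.3.7. The missing Table 4 entry is also certain and can arise after the first session. The upper limit is a lesser matter of an omitted cross-reference, with a literal conflict only at 25 J/cm².

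The consequence is bounded. SAP 4.3 describes schedules optimised for each patient, so doses differ by design. SAP 6.3 only describes the maximum dose and the visit at which it was reached, in about 6 subjects. A reduction does not erase a maximum already delivered, so those two summaries would move only through later sessions; the description of each patient's schedule is affected directly. No test or power figure depends on any of this.

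A reader might go further and infer harm to the primary endpoints, since the minipig text under Figure 1 contrasts light with no light. That text gives the same upper bound, below 0.3 ng/mL, for 8, 10 and 12 J/cm², and the regression in SAP 6.2 uses cumulative drug applied, not light dose. The documents show no effect on the ECG or hypericin endpoints.

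The conclusion assumes only that site staff apply the sentences as written. The point is worth correcting because it concerns a more-than-mild reaction and costs little.

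**What to change.** Three reconciliations are needed. First, the two sentences in 5.3.3 must be reconciled with each other and with 5.3.4 to 5.3.7, on both the strength of the instruction and the minimum step. Second, the reduction rule must be reconciled with the range of Table 4, including a statement of whether doses below 5 J/cm² are intended. Third, the limit in 6.1 should be cross-referenced from the synopsis, 1.4.1 and the 5.3 visit rules. The simplest form is to state the rule once, for example in 6.1, and have every visit section point to it. The content of the rule is for the sponsor and investigator to decide.

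The cost is a protocol wording amendment, with no added visits, samples or data. If sessions have already been run, the clinical study report should record which reading the sites followed and list any dose given outside Table 4.
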